
6) Study Endpoints

The primary study endpoint will be after completion of study (after surgery and survey completion) of 252 patients (126 in each treatment arm). Secondary endpoints include time to PACU clearance and time to hospital discharge. Because the intervention is a single-shot injection, there are no specific safety endpoints. Please see below for a discussion of potential adverse from the pectoralis nerve blocks.

7) Procedures Involved

Subjects presenting for immediate breast reconstruction and meeting inclusion criteria will be approached pre-operatively to make them aware of the study. On the day of surgery, patients will be asked to sign consent for the study. Patients who sign consent will then undergo randomization to a study arm (pre-op placement of intra-op catheter placement). Randomization will be done by study personnel using the i-phone application “Randomizer.” Randomization will follow a blocked scheme; that is, if one patient is randomized to the anesthesia block group, the next will automatically get the catheter treatment. This will ensure equal numbers in both study arms. After consent and randomization is complete, patients will be told of their study arm. Patients will then be asked to fill out a pre-operative pain survey discussing their baseline level of breast pain.

For those randomized to the pre-op placement arm, anesthesia will perform this block prior to surgery but after their pre-operative survey is complete. The anesthesia

PROTOCOL TITLE:

department is already performs pectoralis nerve blocks on selected patients, and have the work flow set up for this. The dose will be 10 mL of 0.25% Ropivacaine for the pecs 1 injection, and 20 mL of 0.25% Ropivacaine for the pecs 2 injection. Ropivacaine is a standard sodium channel blocking anesthetic already FDA approved for peripheral nerve blocks. For those randomized to the intra-operative arm, catheter placement will be performed after the pectoralis muscle flap has been raised, for more accurate targeting of the tissue planes and nerves. Blocks will be performed by the operating surgeon. Instead of single shot blocks, a commercially available On-Q nerve block catheter (Halyard Health, Alpharetta, Georgia) will be placed. Through these catheters, 0.2% Ropivacaine will be instilled at 4 mL/hr for a total of 400 mL (amount in standard On-Q reservoirs). Vitals are continuously monitored in the operative suite and in the Post Anesthesia Care Unit (PACU), with a high level of supervision by the anesthesiology team. In the very rare event of an adverse reaction to the injection, appropriate action will be taken immediately and in accordance with standard work-flow for local anesthetic toxicity (epinephrine for severe allergy or circulatory support, intravascular lipid emulsion and sodium bicarbonate for overdose, although our doses should not be high enough to precipitate this, even with inadvertent intravascular injection). If hypoxia not due to opioids and not responsive to supplemental oxygen is present, a chest radiograph will be ordered to rule out pneumothorax from inadvertent visceral pleural puncture.

Post-operatively, the patients will be monitored in the PACU. They will have standard anesthesia pain and nausea management orders written for (these are ordered en bloc as part of an already existing order set). PACU nursing staff will dose medications according to the written orders. PACU clearance time (which is currently time-stamped in the chart by the PACU resident) will be noted. Often patients will remain in PACU due to ward over-crowding, so actual time of PACU discharge will not be noted. Post-PACU hospital course will proceed as is standard of care, with PRN pain and nausea medication ordered. Standard hospital discharge criteria will be used for all groups.

Information will be collected from all subject's hospital stays, including time in pre-op holding area, time under general anesthesia, duration inhalational anesthetic, amount of narcotic used in morphine equivalents (divided into OR amount, and amounts in first 6, 12, 18 and 24 hours after surgery) after surgery, incidence of nausea/vomiting, number and amount of antiemetic used (same time intervals as above), pain scores overall and by breast on the 0-10 analog scale (average over the same time intervals), time of PACU clearance, and time of hospital discharge. In addition, a RedCaps survey with questions about the patient's pain level will be emailed pre-op and at post-op hours 6,12,24 and days 2-7.

For patients with pain catheters, these catheters will be removed at the patient's regularly scheduled post-operative appointment (generally POD 4 or 5). On-Q balls will not be refilled such that all catheter patients will have infusion for the same amount of time.

One week after hospital discharge, subjects will be emailed a short survey through the RedCap survey system (see supplemental forms for survey questions). Hospital billing

PROTOCOL TITLE:

will be examined with the assistance of the billing department using CPT codes and using publically available cost data.

8) Data and/or Specimen Management and Confidentiality

During the review, the investigator (or research staff) will record data collected in a manner that includes indirect identifiers. Additionally, a single location will include indirect and direct identifiers (to match the two).

To elaborate: Subjects will be identified by a unique study ID (A = pre-op placement, B = intra-op placement; so 1A would be the first patient enrolled in the pre-op placement group). An enrollment log, including a “crib sheet” identifying patients by their study ID and their consent paperwork, will be kept in a binder. That binder will be stored in a locked cabinet in the plastic surgery Lab in Research Building 2. After the IRB has been closed, study consents will be maintained for 3 years, and HIPAA consents for six years, in compliance with IRB rules and regulations. Any data compiled off of the Electronic Medical Record (EMR) will be identified by subject ID only and collected onto a spreadsheet on the PI’s password protected computer.

With respect to the surveys, Redcap is a mature, secure web application that has been used successfully by many other investigators at our institution to collect secure survey data.

Data analysis will be done using <http://vassarstats.net>. Statistical comparisons will be performed across the study groups using T-test for two-group comparisons.

All research personnel will be up to date with their HIPAA training.

For our power analysis, we set our alpha = 0.05 and beta (power) = 0.8. Using the Bashandy et al. paper¹, the mean morphine requirement in the PACU was 2.9 ± 1.861 mg for the Pecs block group, and 6.9 ± 1.861 mg for the control group ($p < 0.001$). Based on our preliminary experience with pre-operatively placed pecs blocks, we estimate that they work well about 70% of the time. If we hope to see a 20% improvement with more accurate plane targeting, then our average morphine requirement in the intra-operative placement group would be 2.3 mg. Therefore, we would have to enroll 126 patients in each arm to have an 80% chance of seeing a difference, if there truly is one.

9) Provisions to Monitor the Data to Ensure the Safety of Subjects

The EMR of every subject who completes the injection portion of this study will be assessed within 24 hours of pectoralis nerve block placement. Any untoward events, such as intravascular injection, allergic reaction, pneumothorax or other unanticipated event will be assessed for its causative relationship to the pectoral nerve block . We anticipate these to all be very unlikely, as the current literature on the pectoralis nerve blocks report a 0% complication rate (see citations, above). If a serious adverse event occurs, these will be reported immediately to the IRB and will be a trigger for an immediate suspension in enrollment and a review of the injection protocol with the Chiefs of both the Departments of Anesthesiology and Surgery. If any performer error can be identified and corrected, then with approval from the departments enrollment will continue. If not, the study will be terminated.

We will cumulatively review the data after 20 subjects in each study arm have been enrolled, and then again at 50 patients, 75 patients, 100 patients, and 126 patients.

10) Withdrawal of Subjects

There are limited circumstances in which a patient would be withdrawn from research, particularly without their consent. The only circumstance would be in the case of aborted tissue expander placement. If the plastic surgeon does not feel that the mastectomy flaps can support the added stress of an expander, then the plastic surgery portion of the procedure is aborted (standard protocol). In this circumstance, the pre-op block arm will already have gotten a block. No intra-operative catheters will be placed. After awakening from anesthesia, the patient will be alerted to their expulsion from the study, and no other data would be collected regarding their hospital stay, and no survey information collected.

Of note, a single patient was enrolled into the control arm of the study prior to this arm being abolished. This patient's survey data has already been collected but will not be used for data analysis. Their hospital data will not be collected.

11) Risks to Subjects

The main foreseeable risk to study subjects is that the nerve block would not work well. In this event, subjects would be appropriately treated with adjunctive pain medications.

Two very rare risks – never reported in the literature, so currently theoretical rather than described – are intravascular injection and pneumothorax, as outlined above. These could have potentially serious consequences, such as bupivacaine toxicity (at worst, leading to hypotension or seizure) or hypoxemia requiring chest tube placement and potentially other procedures. However, pectoralis nerve blocks have been in use for over 5 years, and more risky blocks, including the paravertebral block and intercostal block (both of which have higher rates

PROTOCOL TITLE:

reported of the above complications) for over 30 years. Therefore, these risks are generally considered to be outweighed by the benefits of peripheral blocks.

With respect to the nerve catheters, potential risks to patients with placement are less than with the ultrasound guided block, as these catheters are placed through the skin and into the mastectomy pocket under direct visualization. Additional risks would include the small risk of a post-operative infection related to the catheter. This risk will be minimized by sterile placement, a sterile dressing, and expeditious removal of the catheter within the first post-operative week. As these catheters are standard of care at UC Davis currently, this risk is generally felt to be acceptable.

12) Potential Benefits to Subjects

Study subjects potentially will have decreased anesthetic requirements and improved post-operative pain control. Decreased general anesthesia could mean less postoperative nausea/vomiting. Improved pain control will lead to less narcotic use and therefore may decrease the chance of ileus, nausea, itching and other common narcotic side effects.

13) Sharing of Results with Subjects

No additional information will be shared with subjects.

14) Provisions to Protect the Privacy Interests of Subjects

Patients will be approached about enrolling in this study in the preoperative area. Patient beds in this area are one bed per room; therefore, the conversation will be in private, between the physician and patient. Family members may be present, but this is standard for all preoperative consents (anesthesia consents, block consents, sometimes surgical consents if they are not on file). The consent process will specifically site that refusal to enroll will not result in any penalty, including any withholding of pain medication in the future. Post-operatively, no specific research contact will be made until an online questionnaire is sent out by email.

15) Compensation for Research-Related Injury

There is no specific compensation for study participation. Because breast reconstruction is a planned procedure, all patients undergoing surgery will have insurance. Nerve blocks are a billable procedure, recognized by insurance companies. Any complications related to the procedure will likewise be covered by insurance.

16) Economic Burden to Subjects

As outlined above, the cost of the nerve blocks will be covered by insurance, and no additional out of pocket funds requested. There is no downtime or leave time required for these nerve blocks – in fact, if there is a decrease in narcotic use, then the nerve blocks may even hasten subject's ability to return to work.

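### Section 6 gives a completion milestone as the primary endpoint; the outcome implied by the power paragraph is not designated, not a listed collection window, and not reconciled with Aims 1 and 2B, and sidedness is unstated

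*Combined protocol and SAP*

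**What the plan says.** - **Section 6 (Study Endpoints):** "The primary study endpoint will be after completion of study (after surgery and survey completion) of 252 patients", 126 in each arm. The named secondary endpoints are time to PACU clearance and time to hospital discharge. No opioid or pain outcome appears there.
- **Section 2, Aim 2A:** block efficacy is expected to be significantly better with intra-operative catheters. No measure, window or success criterion is given.
- **Section 2, Aim 2B:** narcotic use is among the secondary outcomes for which no difference is expected. No window is given.
- **Section 2, Aim 1, and Section 8:** efficacy also appears as a proportion, above 90% for all blocks in Aim 1 and about 70% of pre-operative blocks working well in the power paragraph. Success is not defined in either place.
- **Section 8, analysis sentence:** "Statistical comparisons will be performed across the study groups using T-test for two-group comparisons". No variable or sidedness is named.
- **Section 8, power paragraph:** "we set our alpha = 0.05 and beta (power) = 0.8"; "the mean morphine requirement in the PACU was 2.9 ± 1.861 mg for the Pecs block group". A hoped-for gain of 20% is turned into a target mean: "our average morphine requirement in the intra-operative placement group would be 2.3 mg". This leads to 126 per arm.
- **Section 7, data collected:** "amount of narcotic used in morphine equivalents (divided into OR amount, and amounts in first 6, 12, 18 and 24 hours after surgery". Section 7 also says that "PACU clearance time (which is currently time-stamped in the chart by the PACU resident) will be noted", and that the actual PACU discharge time is not recorded.

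**The concern.** A primary endpoint has to be a quantity measured on each patient and compared between arms. The Section 6 entry is neither, so the main comparison has to be inferred from other sections, and those point in different directions.

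Two things are at stake. First, a reader cannot tell whether opioid use, the only outcome with planning figures, is the main test or a secondary outcome expected not to differ. The Aim 2A result could then be chosen from several correlated opioid and pain windows once data are in hand. Free choice of that kind raises the false-positive rate above 5%, by an amount that the documents do not allow to be computed, since they give no variances or correlations for the windows.

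Second, the stated 80% power depends on a sidedness that the plan does not give.

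**Working it through.** **1. Inputs (Section 8, power paragraph).** Alpha 0.05; power 0.80; SD 1.861 mg; reference mean 2.9 mg; 126 per arm. The planned difference is 2.9 − 2.3 = 0.60 mg as written, or 0.20 × 2.9 = 0.58 mg before rounding.

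**2. Reproducing 126.** For two means with equal allocation, n per arm = 2 × SD² × (z_alpha + z_power)² / difference², with SD² = 3.463 and z_power = 0.842.

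- Two-sided (z_alpha = 1.960): 2 × 3.463 × 2.802² / 0.60² ≈ 151.0, so 152. With 0.58 mg it is ≈ 161.6, so 162.
- One-sided (z_alpha = 1.645): 2 × 3.463 × 2.487² / 0.60² ≈ 119.0, so 119. With 0.58 mg it is ≈ 127.3, so 128.

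The exact t-test (noncentral t) gives nearly the same sizes:

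| Test | Difference | n per arm for 80% | Power at 126 per arm |
|---|---|---|---|
| Two-sided | 0.60 mg | 152 | 72.2% |
| Two-sided | 0.58 mg | 163 | 69.3% |
| One-sided | 0.60 mg | 120 | 81.8% |
| One-sided | 0.58 mg | 128 | 79.5% |

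On the morphine figures, 126 lies between the two one-sided sizes and is closest to the one for the unrounded 0.58 mg. Neither two-sided size is near it.

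**3. Power by hand.** The standard error of the difference at 126 per arm is 1.861 × √(2/126) = 0.2345 mg. For 0.60 mg the ratio is 0.60/0.2345 = 2.559. Normal-approximation power is Φ(2.559 − 1.960) = 72.5% two-sided and Φ(2.559 − 1.645) = 82.0% one-sided, in line with the table. The difference detectable with 80% power is (1.960 + 0.842) × 0.2345 = 0.66 mg two-sided, or (1.645 + 0.842) × 0.2345 = 0.58 mg one-sided.

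**4. The passages side by side.**

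| Place | Role of opioid use or efficacy |
|---|---|
| Section 6 | No opioid or pain outcome named |
| Aim 2A | Efficacy expected to differ; measure not given |
| Aim 2B | Narcotic use secondary, no difference expected; window not given |
| Section 8 | PACU morphine, mean 20% lower with catheters |
| Aim 1 and Section 8 | Efficacy as a proportion (>90%; about 70%), success undefined |
| Section 7 | Opioid amounts for OR and first 6, 12, 18 and 24 h; no PACU total |

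No passage says which of these is the Aim 2A outcome. No sample size can be computed for the listed windows, because the documents give no mean or SD for them.

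**5. Reach of an early window.** The infusion in Section 7 runs 400 mL ÷ 4 mL/hr = 100 h. A first-6-hour window covers 6/100 = 6% of that duration.

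**The case against.** The strongest defence is that the plan does have a main outcome in substance. The power paragraph ties the sample size to one variable, one alpha and one target difference, and a t-test is named. That stands in part. A reader might infer that the trial has no primary outcome at all, and the documents do not support so strong a reading. PACU morphine is implied, but not designated, and it is not among the listed collection windows. A PACU total might be obtainable from the chart, since clearance is time-stamped, but the plan does not say so or define the window.

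Three other stronger readings are tempting:

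- *Aim 2B flatly contradicts the power paragraph.* Aim 2B gives no window, so an early difference that disappears later would be consistent with both. No passage says this is meant, so it is an ambiguity to resolve and not a proven contradiction.
- *The cumulative reviews in Section 9 are looks at efficacy.* They sit under a heading on subject safety, after text on adverse events, and the data they cover are not specified. They are not evidence of outcome selection.
- *The sample size is miscalculated.* It is about right for a one-sided test. Aim 2A is directional, but a directional hypothesis does not by itself declare a one-sided test.

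It is also fair to object to a PACU total as primary. Its length may differ by arm: time to PACU clearance is itself a secondary endpoint, and Aim 2B expects a faster course from admission to PACU clearance with intra-operative blocks. If opioid use were proportional to PACU time (an assumption), a 20% shorter stay would alone produce the planned 20% effect. The fix allows for this.

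**Conclusion.** The point holds and must be fixed. The stated primary endpoint cannot be compared between arms. The implied one is undesignated, has no defined window, and is not reconciled with Aim 2B or with efficacy as a success proportion.

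At 126 per arm the stated 80% power is reached, within rounding, only one-sided (79.5-81.8%). A two-sided t-test has 69-72%, a shortfall of about 8 to 11 percentage points. These figures assume that SD 1.861 applies to both arms and to the outcome finally chosen, that the true difference is 0.58-0.60 mg, and that all 126 per arm are analysed.

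The case rests on the conflicting passages and on the power arithmetic, and no size is claimed for the error inflation from choosing among windows.

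**What to change.** Before any comparative data are reviewed:

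1. In Section 6, replace the milestone with one named primary outcome and window for Aim 2A. Choose one of:
   - opioid use in morphine equivalents over the first 6 hours, which is already collected. State as an assumption that the PACU mean and SD carry over, or give new planning figures; or
   - a PACU opioid total with defined start and end, added to the Section 7 list. Report the first-6-hour total alongside it, because PACU time may differ by arm.
2. Define efficacy for Aims 1 and 2A, as a success criterion or as mean opioid use, and use the term consistently in Sections 2 and 8.
3. Make the other opioid and pain windows secondary. Keep time to PACU clearance and time to hospital discharge as secondary.
4. Reword Aim 2B so that it does not predict no difference in the primary outcome. If later windows are meant, name them.
5. State the test as two-sided and restate power at 126 per arm as about 69-72% under the PACU planning figures, or justify a one-sided test.

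**Cost.** Protocol wording and, for a PACU total, up to two chart fields (the total and PACU arrival time). No extra patients are needed if the lower two-sided power is accepted or a one-sided test is justified; keeping 80% two-sided needs about 152-163 per arm, or 26-37 more per arm. Other windows can no longer become the main result. An early window also captures little of the roughly 100 h infusion, so a later catheter benefit would show only in secondary outcomes.

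### Section 6 justifies having no safety endpoints by a single-shot injection, but one arm receives a catheter infusion, and no systematic capture of non-serious complications after 24 hours is described for the safety comparison in Aim 2A

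*Combined protocol and SAP*

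**What the plan says.** - **Aims (Section 2).** Aim 1 reports efficacy and safety and expects no complications. Aim 2A compares safety between the arms and expects no difference.
- **Endpoints (Section 6).** "Because the intervention is a single-shot injection, there are no specific safety endpoints". The next sentence refers the reader onward: "Please see below for a discussion of potential adverse from the pectoralis nerve blocks".
- **Intervention (Section 7).** In the intra-operative arm: "Instead of single shot blocks, a commercially available On-Q nerve block catheter" is placed, through which "0.2% Ropivacaine will be instilled at 4 mL/hr for a total of 400 mL". The reservoir is not refilled. Catheters come out at the patient's "regularly scheduled post-operative appointment (generally POD 4 or 5"). Section 11 speaks of removal within the first post-operative week.
- **Safety monitoring (Section 9).** "The EMR of every subject who completes the injection portion of this study will be assessed within 24 hours of pectoralis nerve block placement". Intravascular injection, allergic reaction and pneumothorax are named, with a general term for other unanticipated events. Serious adverse events go to the IRB at once. Data are reviewed cumulatively at five enrolment points.
- **Risks (Section 11).** Post-operative infection related to the catheter is named as an additional risk.
- **Contact after surgery (Sections 5, 7 and 14).** Pain surveys are emailed at 6, 12 and 24 hours and on days 2 to 7, followed by a satisfaction survey. Section 14 gives emailed questionnaires as the first research contact after surgery.

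**The concern.** The single-shot argument is the only reason given for doing without safety endpoints, and it describes only the pre-operative arm. In the other arm, exposure to the drug and to an indwelling catheter continues for days.

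Safety is also a stated comparison. Aim 2A needs events that are defined in advance and looked for in the same way, over the same period, in both arms. As written, the scheduled search stops at 24 hours, while the catheter remains in place until about POD 4 or 5. A report of no complications, or of no difference, could then describe mainly the first day. Section 11's infection risk is neither among the events named in Section 9 nor among the data items listed in Section 7.

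**Working it through.** **1. The stated reason against the intervention.** Section 6 treats the intervention as one injection. Section 7 gives the intra-operative arm a catheter in place of single-shot blocks. Both statements cannot hold for that arm.

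**2. Length of infusion.** Inputs from Section 7: 400 mL and 4 mL/hr. The protocol prints no duration.
- If 4 mL/hr is the total outflow of one reservoir: 400 / 4 = 100 h.
- If two catheters each run at 4 mL/hr from one reservoir: 400 / (2 × 4) = 50 h.

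The protocol does not say which applies in bilateral cases. A POD 4 removal (about 96 h) can also fall before 100 h, although Section 7 says infusion time is the same for all catheter patients. Those statements need reconciling.

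**3. What the 24-hour check spans.** At most 24/100 = 24% of a 100-hour infusion, or 24/50 = 48% of a 50-hour one. These are shares of exposure time, not of risk.

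**4. Other routes by which a later event could be recorded.**
- Serious adverse event reporting: no time limit, but triggered by an event and confined to serious ones.
- Cumulative reviews: no safety variables are named, and they can show only what has been captured.
- Catheter-removal visit: no safety recording is specified, and removal occurs in one arm only.
- Surveys on days 2 to 7 (six of them) and the satisfaction survey: the schedule makes no distinction between arms, but the content is described as pain and satisfaction. The forms were not supplied.
- Section 7 data list: open-ended, but tied to the hospital stay ("Information will be collected from all subject's hospital stays, including time in pre-op holding area"), whereas removal is at a later appointment.

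None is described as systematic capture of non-serious complications after 24 hours.

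**5. What the anticipated zero-event result could show.** Input: 126 per arm (Sections 6 and 8).
- One arm, exact (Clopper-Pearson) 95% upper limit: 1 − 0.025^(1/126) = 0.0289, or 2.9%.
- Difference, 0/126 v 0/126: at a hypothesised difference d the score statistic is −d / √(d(1 − d)/126). Setting its size to 1.96 gives d/(1 − d) = 3.84/126 = 0.0305, so d = 0.0296. The exact unconditional version, which takes the worst case over the unknown event rate, widens this to about ±3.1 percentage points.

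These limits apply only to the period actually searched.

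**6. Section 9 against Section 10.** Section 9 reviews every subject who completes the injection. Section 10 collects no further hospital-stay data after an aborted expander. By Section 10's own account, only pre-operative-arm patients would already have a block at that point, so any lost safety review falls in one arm.

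**7. End of follow-up.** Section 5 sends the satisfaction survey one week after surgery; Section 7 sends the final survey one week after discharge.

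**The case against.** The strongest defence is that safety is monitored. Section 6 points forward to a discussion of adverse effects. Section 9 has a per-subject check, its sentence on untoward events has no time limit of its own, and serious events are reported whenever they occur. Both arms receive surveys for a week, and the unseen forms might ask about complications. This stands as a limit on the finding: a reader might infer that the trial has no safety monitoring, and the documents do not support that.

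Three other inferences also go too far.

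- *The 24-hour check omits the catheter arm because it refers to the injection portion.* Section 7 calls the surgeon's procedure a block as well ("Blocks will be performed by the operating surgeon"), so the check plausibly covers both arms.
- *The gap biases the comparison toward no difference.* That requires later events to be commoner with the catheter, and no such rate is given. Section 11 says placement risk is lower with the catheter, and the removal visit could add detection in that arm alone, moving the result the other way.
- *Safety counts will be compared by t-test.* The t-test sentence in Section 8 is generic and does not mention safety.

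It can also be argued that Section 10 stops only outcome collection and leaves Section 9's review intact. The text does not say so, and one sentence would settle it.

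None of this repairs the reason given in Section 6 or supplies defined events with equal capture past catheter removal.

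**Conclusion.** The point holds and should be fixed. The reason Section 6 gives for having no safety endpoints is wrong for one of the two arms; confidence in that is high. Aim 2A has no defined safety outcome, and no scheduled safety review with equal capture in both arms is described after 24 hours. Confidence in that gap is moderate, because it assumes that the unsupplied survey forms contain only what the text describes.

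The infusion outlasts the check under either reading of the flow rate (50 or 100 hours). Later non-serious events, including catheter infection, may be missed or found unequally. The documents give no event rates or detection rates from which to derive the direction or size of the resulting bias. The limits of 2.9% per arm and about ±3.1 points assume complete capture, no events and all 126 patients per arm assessed.

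**What to change.** 1. Replace the single-shot rationale in Section 6 with one that fits both arms.
2. Define a safety outcome for Aim 2A from events that can occur in either arm: those named in Section 9, local anaesthetic toxicity, and any post-operative infection recorded without attribution to the catheter. List catheter-specific events descriptively for that arm.
3. Keep the 24-hour check. Add one further record review per patient in both arms, over the same fixed window counted from surgery and running past catheter removal. The sponsor should state its length.
4. Report each arm's proportion, and the difference, with exact 95% confidence intervals.
5. Reconcile Sections 9 and 10 so that subjects already given a block keep their safety review after an aborted expander.
6. Reconcile the final survey timing in Sections 5 and 7 when setting the window.

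**Cost.** One extra record review per patient, a short amendment, and a check that the consent covers the window. Infections due to the surgery itself will be counted in both arms, and events never reported to the site will still be missed. Sample size and clinical management do not change.

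### Opioid and antiemetic amounts to 18 h and 24 h come from the hospital stay only, so earlier discharge truncates them and unequal discharge timing would favour the arm that leaves sooner

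*Combined protocol and SAP*

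**What the plan says.** Section 7 (Procedures Involved) names the source of the clinical data: "Information will be collected from all subject's hospital stays, including time in pre-op holding area, time under general anesthesia". The same sentence goes on to opioid use in morphine equivalents, "divided into OR amount, and amounts in first 6, 12, 18 and 24 hours after surgery", and to antiemetics, "number and amount of antiemetic used (same time intervals as above)". Charted pain is handled differently, as a mean: "pain scores overall and by breast on the 0-10 analog scale (average over the same time intervals)".

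Section 7 applies the hospital's usual discharge criteria to both arms and sets no minimum stay. Section 6 (Study Endpoints) makes discharge an outcome: "Secondary endpoints include time to PACU clearance and time to hospital discharge".

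The only timed collection that does not depend on the patient being in hospital is "a RedCaps survey with questions about the patient's pain level will be emailed pre-op and at post-op hours 6,12,24 and days 2-7", plus a satisfaction survey at about one week. Section 14 (Privacy) confirms that there is no other route: "Post-operatively, no specific research contact will be made until an online questionnaire is sent out by email". The timed survey is described as covering pain level. Nothing says that it asks about doses.

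Section 8 (Data and/or Specimen Management and Confidentiality) names a two-group t-test as the analysis. It gives no rule for a patient whose window is cut short by discharge.

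**The concern.** The windows run on the clock from surgery, but the record stops when the patient goes home. Someone who leaves at 20 h has a 24 h amount built from 20 h of data, and anything she takes in the last 4 h goes unrecorded. If this happens equally in both arms, both amounts are understated and the comparison is roughly fair. If one arm goes home sooner, its recorded use is lower even when hourly use is identical. A difference in discharge time would then be reported twice, once as itself and once as opioid or antiemetic sparing.

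The protocol makes an arm difference in discharge conceivable. Section 3 (Background) cites shorter hospital stay as a benefit of regional blockade, and Aim 2A expects the catheter arm to have the better block. Aim 2B expects no difference in narcotic use, so a truncation artefact could produce a false positive on a comparison where the protocol predicts none.

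**Working it through.** **The plan's own figure.** The 126 per arm in section 8 is built on morphine in the PACU (2.9 mg v 2.3 mg, SD 1.861, alpha 0.05, power 0.80). With n = 2(z_alpha + z_power)² × SD² / delta²:

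- One-sided, with the unrounded 20% reduction (delta 2.9 − 2.32 = 0.58): 128 per arm, within 2 of the stated 126.
- One-sided, delta 0.60: 119.
- Two-sided: 162 (delta 0.58) or 152 (delta 0.60).

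The sidedness is not stated, which is a separate matter. What counts here is that the sample size uses PACU morphine and not the 24 h amount, so truncation at discharge does not touch it.

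**Truncation artefact, simple form.** Assume the same constant hourly use in both arms, and that everyone in an arm leaves at one time, h_later or h_earlier, no later than 24 h. The recorded 24 h amount is proportional to h, so the apparent reduction in the earlier arm is 1 − h_earlier/h_later:

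- 22 h v 22 h: 0
- 22 h v 21 h: 1 − 21/22 = 4.5%
- 22 h v 20 h: 1 − 20/22 = 9.1%
- 22 h v 18 h: 1 − 18/22 = 18.2%

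**Only some leave early.** If a fraction f leaves at h and the rest stay 24 h, the share recorded is 1 − f(24 − h)/24. With 30% v 50% leaving early:

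- h = 18: shares 0.925 and 0.875, apparent reduction 1 − 0.875/0.925 = 5.4%.
- h = 22: shares 0.975 and 0.9583, apparent reduction 1.7%.

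**What the t-test would do.** Simulation with no true difference and 126 per arm: true 24 h use is gamma-distributed with coefficient of variation 0.5, 0.64 or 0.8 (0.64 = 1.861/2.9, borrowed from the PACU figures). Discharge time is normal with SD 2 h, and observation is capped at 24 h. There were 3,000 replicates per case, tested at p < 0.05. All of these settings except the 126 and the 0.64 are assumptions.

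| Mean discharge, two arms | Mean apparent reduction | False-positive rate (range over the three CVs) |
|---|---|---|
| 22 h v 22 h | 0 | 4-5% |
| 22 h v 21 h | about 4% | 6-10% |
| 22 h v 20 h | about 8% | 14-28% |
| 22 h v 18 h | about 17% | 48-85% |

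**Which windows are exposed.** The 24 h amount is affected by any discharge before 24 h, and the 18 h amount only by discharge before 18 h. The 6 h and 12 h amounts are untouched unless patients go home the same day.

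**The case against.** The strongest reply is that the premise is not in the documents. They give no length of stay and do not say that patients leave the next morning. The same discharge criteria apply to both arms, and the time hypothesis in Aim 2B stops at PACU clearance. The length-of-stay benefit cited in the Background concerns regional blockade in general, not one way of placing it against another. All of this stands, and it makes the point conditional. It does not remove the gap: discharge time is free to vary, and the plan has no means of completing a window that it cuts short.

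A reader might also infer more than the documents support:

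- **That the plan scores hours at home as zero use.** It states no such rule. An uncorrected sum would have that effect, but the plan is silent, and the amount could equally be set to missing.
- **That charted pain is biased the same way.** It is an average, so a shorter window does not mechanically lower it. Losing late scores could move it in either direction, and pain is also surveyed by email wherever the patient is.
- **That the artefact matches the 20% effect the trial is planned to detect.** That 20% concerns PACU morphine. The 17-18% figure needs a 4 h gap in mean discharge, which nothing in the documents suggests.

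One caveat remains on the survey side. The one-week survey questions are in supplemental forms that were not available, so an item on doses there cannot be ruled out.

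**Conclusion.** The point holds for the opioid and antiemetic amounts at 18 h and 24 h, and for those only. As described, doses taken after discharge are not captured, and no rule covers incomplete windows. Two conditions are needed for bias between arms: an appreciable number of patients leaving before the window closes, and discharge timing that differs by arm. If either fails, the comparison is not biased in this way, although equal early discharge still understates both arms.

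Under equal, constant hourly use, a gap of 1 to 2 h in mean discharge produces a spurious reduction of about 4% to 9%. In the simulated settings it raises the false-positive rate from about 5% to between 6% and 28%. The 4 h case shows how the artefact grows and is not an expectation. The sponsor can see from recorded discharge times which case applies. Because the fix is cheap and home doses cannot be reliably recovered later, the change should be made while patients are still being enrolled.

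**What to change.** - Add one item to the 24 h REDCap survey that is already sent: opioid and antiemetic doses taken since discharge (drug, number, time). Convert the opioids to morphine equivalents and add the doses to the inpatient 18 h and 24 h amounts for all randomised patients.
- State in section 8 that hours after discharge are not treated as zero use, and that an unanswered item is recorded as missing.
- Do not restrict the 18 h and 24 h comparisons to patients still in hospital. That selects on a post-randomisation outcome and would replace truncation with selection bias.
- Report the number per arm discharged before 18 h and before 24 h.
- Give use per hour observed as a sensitivity check only. It is neutral only if hourly use is constant. If use falls over time, patients who leave early show a higher rate and the bias reverses.

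The cost is protocol wording and one survey item. The downside is that home doses are self-reported and some will be missing.
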